10.1 Adverse Events

Adverse events will be coded by system organ class (SOC) and preferred term (PT) using the Medical Dictionary for Regulatory Activities (MedDRA).

An AE that occurs during the Open-label Treatment Period will be considered a treatmentemergent AE (TEAE) if it starts as a new event or if its severity increases during the Open-label Treatment Period. An AE that occurs more than 1 day after the date of the last dose of open-label lumateperone will not be counted as a TEAE.

The number and percentage of patients reporting TEAEs will be tabulated by system organ class (SOC) and PT; by SOC, PT, and severity; and by SOC, PT, and relationship to study drug. If more than one AE is coded to the same preferred term for the same patient, the patient will be counted only once for that preferred term using the most severe and most related occurrence for the summary by severity and by relationship to study drug.

The incidence of common (\geq 5% of patients) TEAEs will be summarized by preferred term and treatment group.

The number and percentage of patients reporting serious AEs (SAEs) during the Open-label Treatment Period will be tabulated by SOC and PT. Also, the number and percentage of patients reporting AEs leading to drug withdrawal will be tabulated by SOC and preferred term. Listings will be presented for patients with SAEs, patients with AEs leading to drug withdrawal, and patients who died.

The incidence of extrapyramidal symptom (EPS) TEAEs will be summarized by PT and treatment group and will be sorted by decreasing frequency. The PTs for EPS will be based on Broad and Narrow Standardised MedDRA Queries (SMQs) as listed in Table 10-1. The analysis for EPS TEAEs based on Broad SMQs will also include the preferred terms listed under Narrow SMQs.

Confidential Page 18 of 40

Table 10-1: Preferred Terms for Extrapyramidal Symptoms

Scope	Preferred Terms
Narrow	Akathisia, Athetosis, Ballismus, Buccoglossal syndrome, Chorea, Choreoathetosis, Dopamine, dysregulation syndrome, Dyskinesia, Dyskinesia neonatal, Dyskinesia oesophageal, Grimacing, Oculogyric crisis, Pharyngeal dyskinesia, Protrusion tongue, Rabbit syndrome, Respiratory dyskinesia, Tardive Dopa-responsive dystonia, Dystonia, Dystonic tremor, Early onset primary dystonia, Emprosthotonus, Meige's syndrome, Oculogyric crisis, Opisthotonus, Oromandibular dystonia, Pharyngeal dystonia, Pleurothotonus, Spasmodic dysphonia, Torticollis, Trismus, Writer's cramp, Akinesia, Bradykinesia, Cogwheel rigidity, Freezing phenomenon, Hypertonia, Hypertonia neonatal, Hypokinetic dysarthria, Muscle rigidity, On and off phenomenon, Parkinsonian crisis, Parkinsonian gait, Parkinsonian rest tremor, Parkinsonism, Parkinsonism hyperpyrexia syndrome, Parkinson's disease, Parkinson's disease psychosis, Propulsive gait, Resting tremor.
Broad	All preferred terms listed under Narrow (above) plus the following: Extrapyramidal disorder, Hyperkinesia, Hyperkinesia neonatal, Motor dysfunction, Movement disorder, Psychomotor hyperactivity, Restlessness, Abnormal involuntary movement scale, Chronic tic disorder, Complex tic, Drooling, Muscle twitching, Provisional tic disorder, Secondary tic, Tic, Blepharospasm, Facial spasm, Gait inability, Laryngospasm, Muscle contractions involuntary, Muscle spasms, Muscle spasticity, Muscle tightness, Muscle tone disorder, Musculoskeletal stiffness, Oesophageal spasm, Oropharyngeal spasm, Posture abnormal, Posturing, Provisional tic disorder, Risus sardonicus, Tongue spasm, Torticollis psychogenic, Uvular spasm, Action tremor, Bradyphrenia, Dysphonia, Fine motor skill dysfunction, Gait disturbance, Hypokinesia, Hypokinesia neonatal, Laryngeal tremor, Micrographia, Mobility decreased, Postural reflex impairment, Postural tremor, Reduced facial expression, Tremor, Tremor neonatal, Walking disability.

Confidential Page 19 of 40

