
Confidential Page 11

background ADT, oral administration.

Mode of Administration

Criteria for Evaluation	
Safety Measures	AE recording, clinical laboratory measures, vital signs, electrocardiograms (ECGs), and physical examination; measures of extrapyramidal symptoms: Abnormal Involuntary Movement Scale (AIMS), Barnes Akathisia Rating Scale (BARS), and Simpson Angus Scale (SAS); Columbia-Suicide Severity Rating Scale (C-SSRS); and pregnancy test (if applicable).
Efficacy Endpoints	Change from baseline in MADRS total score and CGI-S score.
Pharmacokinetic Measures	Optional blood samples for pharmacokinetic (PK) analysis of lumateperone and metabolites (IC200131, IC200161, IC200565, IC201308, and IC201309) will be collected. Three blood samples will be collected at Visit 2 at predose, between 0.5-to-1-hour postdose, and between 1.5 to 3 hours postdose. One sample will be collected at Visit 7.
Statistical Methods and Sample Size	Approximately 760 patients will be enrolled. The sample size is not based on statistical considerations, but is based on the number of patients who may be eligible based on participation in the lead-in study. It is expected that the majority of patients who safely complete the lead-in study will continue treatment for the full 26 weeks.
	All safety parameters will be summarized descriptively. Safety analyses will be based on the Safety Population defined as all patients who received at least one dose of open-label lumateperone 42 mg.
	Analyses of efficacy endpoints will be performed based on the patients in the Safety Population who have an available baseline efficacy value and at least one postbaseline efficacy assessment during the Open-label Treatment Period. Analyses will primarily consist of change from baseline descriptive summaries of MADRS total score and CGI-S scores.
	Individual plasma concentrations of lumateperone and metabolites will be listed and summarized by visit/timepoint. Plasma concentrations of lumateperone and potentially of selected metabolites will be analyzed using a population PK approach. The results from the population PK analyses will be presented in a separate report.

Table 1-1: Schedule of Evaluations

Study Period	Screening /Baseline Visit ¹		Open-label Treatment Period ² Fo													Safety Follow Up	
Visit Number	1	2	3	4	5	6	7	8	9	10	11	12	13	14	15	16/ET	17
Study Day	1	8	15	22	29	43	57	71	85	99	113	127	141	155	169	183	197

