2. INTRODUCTION

This statistical analysis plan (SAP) provides the technical and detailed elaboration of the statistical analyses of the efficacy and safety data as outlined and/or specified in the Protocol Amendment 1 (dated 23 Aug 2021) of Study ITI-007-503.

Study ITI-007-503 ("Study 503") is an international, open-label, multicenter, 6-month study to assess the safety and tolerability of lumateperone as adjunctive therapy in patients with MDD. The Study will be performed at approximately 120 study centers. No *de novo* patients will be enrolled.

Patients who have safely completed the lead-in studies may be eligible to participate in this Open-label Safety Study. Lead-in study completion is defined as a patient who completes the double-blind treatment period (ie, all scheduled visits up to and including Visit 8) of the lead-in study.

The study will be conducted as follows:

- A Screening Period of one day in duration. Potential patients rolling over from the lead-in studies will be evaluated for eligibility during the Screening/Baseline Visit (Visit 1/Day 1) which is the same visit as Visit 8/Day 43 of the lead-in study. Patients who meet all eligibility criteria at the Screening/Baseline Visit (Visit 1/Day 1) will be dispensed lumateperone 42 mg to be self-administered each evening without respect to food.
- A **26-week Open-label Treatment Period** during which patients will self-administer lumateperone, to be taken each evening, without respect to food. Background ADT should also continue as previously prescribed, with no change of dose from the lead-in studies. Patients will attend visits on Weeks 1, 2, 3, 4, 6, 8, 10, 12, 14, 16, 18, 20, 22, 24, and 26. The Open-label Treatment Period will last a total of 26 weeks. A patient will be defined as a treatment completer if the patient completes the Open-label Treatment Period (all scheduled visits up to and including Visit 16/Week 26).
- A 2-week Safety Follow-up Period. A Safety Follow-up visit will occur approximately 2 weeks after completion of the Open-label Treatment Period or after the Early Termination (ET) Visit. Any ongoing AEs at the Safety Follow-up Visit must be followed until resolution, until the AE stabilizes, until it is determined to be not clinically significant, or until the patient is lost to follow-up.

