- An unscheduled urine drug test may be conducted at any time during the study at the Investigator's discretion.
- Female patients of childbearing potential must have a negative urine pregnancy test. Because the Screening/Baseline Visit (Visit 1/Day 1) serum pregnancy test results will not be available at the Screening/Baseline Visit (Visit 1/Day 1), patients will be discontinued immediately upon receipt of a positive serum pregnancy test result. For all other visits, a urine pregnancy test will be performed. Unscheduled pregnancy tests may be administered at any time during the study at the Investigator's discretion.

Confidential Page 9 of 40

- Patients who consent to PK sampling will take the evening dose the day before Visit 2; the date and time of this dose should be recorded as reported by the patient. At Visit 2, patients will be administered the Visit 2 dose of lumateperone at the study site after an overnight fast of at least 10 hours and will continue to fast for at least 2 hours after dosing. The date and time of lumateperone administration at Visit 2 must be recorded. PK sampling will be collected at Visit 2 at predose (within 30 minutes prior to dosing), between 0.5 hour and 1-hour post-dose and between 1.5 hour and 3 hours post-dose. The date and time of PK sample collection at each timepoint must be recorded. Patients will be instructed not to take an evening dose of lumateperone at Visit 2. The next dose of lumateperone should be taken the next evening as prescribed. ADT should be taken as prescribed throughout the PK sampling period.
- Patients who consent to PK sampling will have one blood sample collected at Visit 7. The patient-reported date and time of lumateperone administration prior to PK sampling on the evening before Visit 7 should be recorded. The date and time of PK sample collection must be recorded.

Antidepressant prescriptions will be provided to patients as needed through the duration of the study.

Confidential Page 10 of 40

3. STUDY OBJECTIVES

The primary objective of the Open-label Safety Study is to evaluate the safety and tolerability of lumateperone 42 mg administered orally once daily for approximately 26 weeks as adjunctive treatment to ADT in patients with MDD.

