4.2 Safety Population

Safety Population includes all patients in the Enrolled Population who receive at least one dose of open-label lumateperone.

Confidential Page 12 of 40

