8. EXTENT OF EXPOSURE AND TREATMENT COMPLIANCE

8.1 Extent of Treatment Exposure

Exposure to open-label lumateperone for the Safety Population will be summarized for treatment duration, calculated as the number of days from the date of the first dose of open-label lumateperone taken to the date of the last dose taken, inclusive. The number and percentage of patients with each treatment duration category will be summarized, respectively.

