9.2 CGI-S Score

A descriptive summary for the change from baseline to each assessment visit in CGI-S score will be provided for each scheduled visit.

Confidential Page 17 of 40

10. SAFETY ANALYSES

Safety analyses will be performed using the Safety Population. The safety parameters will include AEs, clinical laboratory, vital signs, ECG, and EPS (AIMS, BARS, and SAS) and C-SSRS scales. Baseline is defined as the last measurement prior to the first dose of double-blind treatment during the lead-in studies (Studies ITI-007-501 and ITI-007-502).

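### SAP 10.1 reports adverse events only as crude percentages of all dosed patients, which can fall short of the risk over a full 26 weeks on drug

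*SAP*

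**What the plan says.** The primary objective (SAP section 3) is "to evaluate the safety and tolerability of lumateperone 42 mg administered orally once daily for approximately 26 weeks" as an adjunct to antidepressant therapy. SAP section 10 says "Safety analyses will be performed using the Safety Population", and SAP 4.2 defines that set: "Safety Population includes all patients in the Enrolled Population who receive at least one dose of open-label lumateperone". No minimum exposure is required.

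For adverse events, SAP 10.1 states: "The number and percentage of patients reporting TEAEs will be tabulated by system organ class (SOC) and PT". SAEs and AEs leading to drug withdrawal are also given as number and percentage. Common TEAEs (at least 5% of patients) and EPS TEAEs are given as incidence. The counting window for TEAEs closes individually for each patient: "An AE that occurs more than 1 day after the date of the last dose of open-label lumateperone will not be counted". The planned length is fixed (SAP section 2): "The Open-label Treatment Period will last a total of 26 weeks".

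Exposure is handled separately. SAP 8.1 says "Exposure to open-label lumateperone for the Safety Population will be summarized for treatment duration", in days from first to last dose and in categories. SAP section 5 reports completion and reasons for discontinuation. Protocol 6.5 rules out replacing patients who leave.

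Neither document plans a patient-year denominator, a time-to-first-event estimate, a cumulative incidence or AE incidence by time interval. Protocol 9.4.5.1 leaves further AE detail to the SAP, which adds none of these. Neither document says which risk the percentages are meant to estimate.

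**The concern.** With one arm and no control, the absolute frequency of each event is the main safety result. Patients contribute very different amounts of time at risk, and the crude percentage takes no account of this. A patient who leaves at Week 2 without an event has the same weight in the denominator as one observed to Week 26.

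Much of the expected loss need not be caused by adverse events. Protocol 6.4.1 allows withdrawal for lack of efficacy, and Protocol 7.9 requires discontinuation when a new depression treatment is started. Such exits remove time at risk without adding an event. Protocol 6.2.1 justifies the study as extending what was learned from acute treatment, so events that emerge later matter most here, and they are the ones most affected. The 5% cut for the common-TEAE table also uses the crude figure.

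**Working it through.** The plan states no event rate, dropout rate or precision for adverse events, and the planned enrolment of about 760 is explicitly not based on statistical considerations. There is therefore no figure of the plan's own to reproduce. The check asks how far a crude percentage can fall below the risk had everyone stayed on drug.

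**Inputs from the documents:** treatment period 26 weeks; denominator all dosed patients; counting stops 1 day after last dose; no replacement; about 760 patients.

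**Assumed inputs:** true 26-week risk R = 10%; dropout by Week 26 of 10% to 49%, independent of the event. The only guide to dropout is the Protocol synopsis: "It is expected that the majority of patients who safely complete the lead-in study will continue treatment for the full 26 weeks". I read this as dropout below one half. It is an expectation, not a limit, and Protocol 9.2 and SAP section 13 expect only that a majority will take part.

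**Constant hazards.** Over the 26 weeks let l = −ln(1 − R) and d = −ln(1 − dropout). Then

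crude = l/(l + d) × [1 − exp(−(l + d))].

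With R = 10%, l = 0.1054:

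- 20% dropout: d = 0.2231; 0.1054/0.3285 × (1 − 0.9 × 0.8) = 0.3207 × 0.28 = 9.0%
- 30% dropout: d = 0.3567; 0.1054/0.4620 × (1 − 0.9 × 0.7) = 0.2280 × 0.37 = 8.4%
- 40% dropout: d = 0.5108; 0.1054/0.6162 × (1 − 0.9 × 0.6) = 0.1710 × 0.46 = 7.9%

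**Onset timing.** The same model was run with the event hazard confined to Weeks 0–4 or to Weeks 13–26, keeping the true 26-week risk at 10%. For the late case, with h = −ln(0.9)/13 and m = d/26 per week, crude = exp(−13m) × h/(h + m) × [1 − exp(−13(h + m))].

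| Dropout by Week 26 | Constant hazard | Onset Weeks 0–4 | Onset Weeks 13–26 |
|---|---|---|---|
| 10% | 9.5% | 9.9% | 9.3% |
| 20% | 9.0% | 9.8% | 8.5% |
| 30% | 8.4% | 9.7% | 7.7% |
| 40% | 7.9% | 9.6% | 6.9% |
| 49% | 7.3% | 9.5% | 6.1% |

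Across this dropout range the relative loss is 5% to 27% under constant hazard, 1% to 5% for early onset and 8% to 39% for late onset. With no dropout there is none. The constant-hazard losses are similar for true risks from 5% to 40%.

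**The 5% cut.** Under constant hazard, an event needs a true 26-week risk of 5.3%, 5.9% or 6.8% to reach a crude 5% at 10%, 30% or 49% dropout.

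**What an added rate would show.** With R = 10%, the true rate is 0.1054/26 × 365.25/7 × 100 = 21.1 per 100 patient-years. In 2,000 simulated studies of 760 patients with 30% independent dropout, the average crude percentage was 8.5%, the average Kaplan-Meier risk at Week 26 was 10.0%, and the average rate was 21.2 per 100 patient-years.

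**The case against.** The strongest reply is that nothing is biased. SAP 10.1 counts events on treatment and stops 1 day after the last dose. For risk while on treatment, stopping drug is a competing event and the crude percentage is a valid estimate. This stands. A reader might infer that the tables understate 26-week risk outright, or that a patient who leaves at Week 2 is recorded as event-free for 26 weeks. The documents support neither reading. That patient is recorded as having no TEAE while treated, and a patient who leaves because of a TEAE is already in the numerator. The shortfall exists only against the risk had treatment continued, with dropout unrelated to the event.

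Other parts of the reply also stand:

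- The size rests on assumed dropout.
- Duration and disposition are tabulated, so a reader can see that follow-up was unequal, though those tables cannot be turned into event-specific rates.
- Late weight gain and dyskinesia do not depend on the AE table alone: weight and AIMS changes are summarised by visit (SAP 10.3 and 10.5.1).
- It would be too strong to say that the percentages cannot be set beside lead-in or one-year data, or that patient-year rates would settle it. The SAP plans no such comparison, and when the hazard falls over time a longer study gives a lower rate.
- Kaplan-Meier is unsuitable for AE withdrawal. It would censor patients who stop for lack of efficacy or withdrawn consent, which are competing events, and so overstate the proportion withdrawing for AEs. Sponsor or site termination aside, the crude proportion already estimates that quantity.

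The plan is descriptive, and no hypothesis test uses these percentages.

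**Conclusion.** The point holds in conditional form, as a worthwhile minor improvement. SAP 10.1 gives only crude percentages, does not say that they describe on-treatment risk, and never links the exposure days of SAP 8.1 to events. For a true 10% risk with constant hazard and independent dropout, the shortfall is about 1.0, 1.6 or 2.1 percentage points at 20%, 30% or 40% dropout. It is near zero for early onset and larger for late onset. The actual size cannot be derived from the documents, because they give no dropout rate. The planned tables are not wrong and should stay.

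**What to change.** 1. Keep every planned crude table. State in SAP 10.1 that the percentages describe risk while on open-label treatment.
2. For any TEAE, common TEAEs, SAEs, AEs leading to withdrawal and EPS TEAEs, add the number of patients with a first event per 100 patient-years at risk, with a 95% confidence interval. Time at risk runs from first open-label dose to the first event or, without one, to last dose + 1 day.
3. Optionally, add a Week 26 Kaplan-Meier estimate for any TEAE, labelled as the risk if treatment had continued and as assuming independent dropout. Do not use Kaplan-Meier for AE withdrawal.

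The cost is a few columns. Dose dates are already needed for SAP 8.1, and AE start dates already have imputation rules, so no new data are required. Two downsides should be noted with the tables. Patient-year rates assume a constant rate and can mislead for early-onset events. SAP 15.6 also sets some partial or missing AE start dates to the first-dose date, which shifts onset earlier and affects time at risk more than it affects a crude percentage.

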1. PROTOCOL SYNOPSIS AND SCHEDULE OF EVALUATIONS

CLINICAL STUDY SYNOPSIS:	Study ITI-007-503
Title of Study	An Open-label, Multicenter Trial to Assess the Safety and Tolerability of Lumateperone as Adjunctive Therapy in the Treatment of Patients with Major Depressive Disorder
Study Centers (Country)	Approximately 120 study centers (US and Non-US)
Development Phase	Phase 3
Objectives	Primary Objective To evaluate the safety and tolerability of lumateperone 42 mg administered orally once daily for approximately 26 weeks as adjunctive treatment to antidepressant therapy (ADT) in patients with major depressive disorder (MDD). Secondary Objectives To evaluate whether lumateperone 42 mg administered orally once daily for approximately 26 weeks as adjunctive treatment to ADT improves or maintains improvement of depressive symptoms in patients with MDD as measured by change from baseline in the Montgomery-Åsberg Depression Rating Scale (MADRS) total score and in the Clinical Global Impression Scale-Severity (CGI-S) score.
Study Design	This is an international, multicenter, open-label, fixed dose, 26-week study of patients with MDD. Eligible patients from the lead-in studies will enter the Open-label Safety Study at the Screening/Baseline Visit (Visit 1/Day 1), at which point patient eligibility will be assessed and informed consent obtained. At the Screening/Baseline Visit (Visit 1/Day 1), which is the same visit as Visit 8/Day 43 of the lead-in study, eligible patients will receive open-label lumateperone 42 mg once daily for approximately 26 weeks. Patients will continue their background ADT from the lead-in study. Patients will be seen for weekly visits through Visit 5/Week 4. Thereafter, visits will occur every two weeks. A Safety Follow-up visit will occur on Visit 17/Day 197, approximately 2 weeks after the last dose of open-label lumateperone 42 mg.
Number of Patients	Approximately 760 patients are planned to be enrolled in the Open-label Safety Study. No de novo patients will be enrolled.

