6.2 Scientific Rationale for Study Design

6.2.1 Study Design

Long term maintenance treatment of depression beyond the acute exacerbation of illness is standard of care, as MDD is for many patients a chronic, relapsing illness. Therefore, a longer-term, open label study to undertake safety monitoring and efficacy evaluations for periods greater than the time required to treat the symptoms of a depressive episode is warranted. This study allows patients who have participated in the double blind lead-in studies to start or continue treatment with lumateperone for up to 6 months, which is considered an adequate amount of time to collect safety, tolerability, and efficacy data to further the information gained in the acute treatment exposures.

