Alkaline phosphatase	U/L	_	≥ 2 × ULN		
ALT	U/L	_	≥ 3 × ULN		
AST	U/L	_	≥ 3 × ULN		
Blood urea nitrogen (BUN)	mg/dL	_	≥ 30		
Calcium	mg/dL	< 7	> 12		
Chloride	mEq/L	< 90	> 115		
Total Cholesterol	mg/dL	_	≥ 300		
СРК	mg/dL	_	≥ 5 × ULN		
Creatinine	mg/dL	_	> 1.3 × ULN		
Glucose	mg/dL	< 45	> 160		
LDL Cholesterol	mg/dL	_	> 200		
Potassium	mEq/L	< 3	> 5.5		
Prolactin	ng/ml	_	> 200		
Sodium	mEq/L	< 130	> 150		
Total bilirubin	mg/dL	_	≥ 2 × ULN		
Total protein	_	< 0.9 × LLN	> 1.1 × ULN		
Triglycerides	mg/dL	_	≥ 300		
Uric Acid	mg/dL	_	> 1.1 × ULN		
Urinalysis					
Protein	_	_	At least 2 +		
Glucose	_	_	At least 2 +		
Blood	_	_	At least 2 +		

ALT = alanine aminotransferase; AST = aspartate aminotransferase; CPK=creatine phosphokinase; LLN = lower limit of normal of laboratory reference range; PCS = potentially clinically significant; ULN = upper limit of normal of laboratory reference range.

Confidential Page 21 of 40

^a Criteria refer to conventional units.

The number and percentage of patients with shifts from baseline at the end of Open-label Treatment Period according to normal range and PCS criteria (PCS Low, Low, Normal, High, PCS High) for each parameter will be provided if applicable.

The criteria for elevated liver function-related laboratory values are specified in Table 10-3. The frequency and percentage of subjects with treatment-emergent elevated liver function values during the Open-label Treatment Period will be summarized for each treatment group for the Safety Population.

Table 10-3: Elevated Liver Function Criteria

Liver Function Parameter	Criteria
	\geq 3 × ULN
ALT	\geq 5 × ULN
ALI	$\geq 10 \times ULN$
	\geq 20 × ULN
	\geq 3 × ULN
AST	\geq 5 × ULN
ASI	$\geq 10 \times ULN$
	\geq 20 × ULN
ALT or AST	\geq 3 × ULN
	\geq 5 × ULN
	$\geq 10 \times ULN$
	\geq 20 × ULN
Total Bilirubin	$\geq 1.5 \times ULN$
	\geq 2 × ULN
Alkaline phosphatase	$\geq 1.5 \times ULN$
	\geq 2 × ULN
Combined Elevation in ALT or AST, and Total	ALT or AST \geq 3 × ULN, Total
Bilirubin	Bilirubin $\geq 1.5 \times ULN$
	ALT or AST $\geq 3 \times ULN$, Total
	Bilirubin ≥ 2 × ULN
Hy's Law	Concurrent evaluation ^a :
	ALT or AST $\geq 3 \times \text{ULN}$, Total
	Bilirubin $\geq 2 \times ULN$, and Alkaline phosphatase $\leq 2 \times ULN$
	phosphatase > 2 ^ OLN

^a Concurrent assessments: analytes may come from multiple samples taken within a 24-hour period.

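### Two adverse event tables and the liver table use an undefined treatment group, and no table separates patients starting lumateperone from those continuing it

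*SAP*

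**What the plan says.** Protocol Section 1 (synopsis) describes one regimen: "eligible patients will receive open-label lumateperone 42 mg once daily for approximately 26 weeks". Protocol 6.2.1 says that the study allows lead-in patients "to start or continue treatment with lumateperone for up to 6 months", so both new starters and continuing patients are expected.

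The safety tables in the SAP are grouped in two ways:

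- **By treatment group.** In SAP 10.1 the common (5% or more) TEAEs "will be summarized by preferred term and treatment group", and the EPS "TEAEs will be summarized by PT and treatment group and will be sorted by decreasing frequency". In SAP 10.2 the liver elevations "will be summarized for each treatment group for the Safety Population".
- **With no group named.** For the main tables in SAP 10.1, "The number and percentage of patients reporting TEAEs will be tabulated by system organ class (SOC) and PT", with further versions by severity and by relationship. The serious-event table covers the open-label period by system organ class and preferred term only. The table of events leading to withdrawal is specified in the same way.

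Neither document defines a treatment group, and no summary in either is specified by lead-in treatment. SAP 8.1 counts exposure "from the date of the first dose of open-label lumateperone taken to the date of the last dose taken", so lumateperone taken in the lead-in does not appear.

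**The concern.** A programmer cannot tell from the SAP whether the three tables need one column or several. More importantly, the two kinds of patient differ in ways that bear on adverse events:

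- Entry requires safe completion of the lead-in (Protocol 6.3.1). Among patients who were on lumateperone, this selects for those who tolerated it.
- SAP 10.1 counts a TEAE only if it is new or becomes more severe in the open-label period. An early effect that began in the lead-in and continued unchanged is not counted.

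Safety and tolerability is the primary objective. A reader may take the pooled percentage as the rate for a patient starting the drug, and for early-onset events it may be too low for that use.

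**Working it through.** The plan has no figure to reproduce. The sample size of about 760 has no statistical basis (Protocol 9.2, SAP 13), and all safety summaries are descriptive.

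**Step 1. What treatment group could mean.** Protocol 9.4.1 summarizes disposition by treatment group and study center. The matching sentence in SAP 5 drops treatment group, yet the term remains in the three safety tables. It could be leftover wording or could mean lead-in arm. The text does not settle which.

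**Step 2. Exposure history.** Open-label Visit 1 is Day 43 of the lead-in (Protocol 6.1). Continuers therefore enter with about 42/7 = 6 weeks of drug and may reach about 6 + 26 = 32 weeks. Starters reach about 26 weeks.

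**Step 3. Effect of pooling.** Let p be the TEAE rate in starters, f the share of starters, and r the continuer rate divided by the starter rate. None of these is in the documents. I assume f = 0.4 to 0.6 and vary r.

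Pooled rate = f·p + (1 − f)·r·p, so pooled/starter = f + (1 − f)·r.

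| r | f = 0.4 | f = 0.5 | f = 0.6 | Pooled against starter rate |
|---|---|---|---|---|
| 0.5 | 0.70 | 0.75 | 0.80 | 20% to 30% lower |
| 0.75 | 0.85 | 0.875 | 0.90 | 10% to 15% lower |
| 1.0 | 1.00 | 1.00 | 1.00 | equal |
| 1.25 | 1.15 | 1.125 | 1.10 | 10% to 15% higher |

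For example, with p = 10%, f = 0.5 and r = 0.5, the pooled rate is 0.5 × 10% + 0.5 × 5% = 7.5%.

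**Step 4. The 5% cut.** The pooled rate falls below 5% when p < 5%/[f + (1 − f)·r]. At r = 0.5 the limits are 5%/0.70 = 7.1%, 5%/0.75 = 6.7% and 5%/0.80 = 6.3% (f = 0.4, 0.5, 0.6). At r = 0.75 they are 5.9%, 5.7% and 5.6%. A starter rate between 5% and the limit would be left out of a common-TEAE table based on the pooled rate.

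**Step 5. Precision after a split.** The 95% half-width is 1.96·√[p(1 − p)/n]. If half of 760 are starters (n = 380), it is 1.96·√(0.05 × 0.95/380) = 2.2 points at a 5% rate and 3.0 points at 10%. For all 760 it is 1.6 and 2.1 points. With 304 to 456 starters it is 2.5 to 2.0 points at a 5% rate.

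**The case against.** The strongest reply is that the plan does what it sets out to do. The objective is safety over about 26 weeks in this cohort, not risk at first exposure, and the pooled rate describes the cohort correctly. That stands. The pooled column should stay, and the point concerns what else is shown.

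A reader might infer that pooling does understate first-exposure risk. The documents do not support that. It needs a lower rate in continuers, and no rate by lead-in arm is given. Starters also had to complete the lead-in safely, so background early events may be depleted in both groups. Only drug-related early events would be expected to differ. For late or cumulative events the difference could be nil or reversed.

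A reader might also infer that an event below 5% is lost. It is not, because the full TEAE tables by system organ class and preferred term, and the EPS table, carry no frequency cut. The event leaves one display only.

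Finally, a reader might extend the argument to laboratory, potentially clinically significant value and C-SSRS tables. It does not carry over unchanged. Their baseline precedes the first lead-in dose (SAP 10 and 10.5.4), so an abnormality that arose in the lead-in and persists can still be counted.

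**Conclusion.** The undefined term is certain and affects three tables: common TEAEs, EPS TEAEs and liver elevations. It is equally certain that no table is specified by lead-in treatment and that the Safety Population mixes two exposure histories. That pooled rates understate early-onset events in new starters is plausible but not shown. Its direction rests on continuers having the lower rate, and its size on the assumed share of starters and rate ratio in Step 3. The split is worth making whichever way the rates fall: similar rates would be visible side by side, and a difference would no longer be hidden.

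**What to change.** - **SAP 10.1:** Define treatment group as lead-in assignment (not on lumateperone in the lead-in; on lumateperone in the lead-in). The documents do not name the lead-in comparator, so the labels should follow the lead-in protocols. Show these two columns beside an overall column in the TEAE, common-TEAE, serious-event, withdrawal and EPS TEAE tables.
- **Common-TEAE table:** Include a term if it reaches 5% in either group or overall.
- **SAP 10.2 liver table:** Use the same definition or delete the phrase.
- **SAP 8.1:** Keep open-label exposure, and add total lumateperone exposure including the lead-in for continuing patients.

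The cost is extra columns, a merge of lead-in treatment and exposure data, and wider intervals per group (about ±2.2 points at a 5% rate with 380 patients, against ±1.6 for all 760). Patients keep their lead-in ID (Protocol 7.4), so the merge is simple once lead-in assignments are available. No new data collection in this study is needed.
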